## II. SPECIFIC AIMS

The primary aim of this pilot study is to evaluate the **effects** of standard physical therapy compared to treatment with SWT, and a combination of SWT and PBMT (each combined with physical therapy) in the management of Achilles tendinopathy. *We hypothesize runners in each treatment allocation will see improvement in functional outcomes, pain and measures of Achilles tendon structure compared to baseline measures. As SWT and PBMT may change structural properties and modulate pain in tendinopathy, we anticipate greater measures in running function for participants assigned to SWT and PBMT in treatment over physical therapy as sole treatment.*

The secondary outcome will be to evaluate cross-over response. After the initial 3-month randomized control trial, subjects who are not satisfied with results, will be able to select a different treatment arm for the remaining 3 months of the study.

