**V. STUDY PROCEDURE**

**a. Overall Research Design and Methods**

This study has been split into two parts. **Part 1 is the initial randomized control trial, and Part 2 is when the participants can select the treatment they want to receive if they are not satisfied with their initial treatment.** In Part 1 patients will not be blinded to the treatment arm that they receive due to the obvious differences in the treatments.

Participants will also be asked to log their return to running at home using the University of Delaware Return to Sport protocol.

*Part 1*

Study participants will be randomly assigned to one of three treatment groups, using a block randomization generator **that is implemented into REDCap**. There will be 20 patients per treatment group, no power calculation as this is a feasibility study. The three treatment arms are: physical therapy only, SWT and physical therapy, and a combination of SWT, PBMT and physical therapy. All runners, regardless of treatment group, will be asked to enroll in physical therapy at a location that is convenient to them (and accepts their insurance if applicable) and complete a standard physical therapy program addressing individual strength deficits in both proximal (spine and hip girdle) along with distal (thigh, leg and foot/ankle) muscle groups. To standardize loading program, we will provide all runners with an at-home exercise program designed by [name] for progressive Achilles tendon loading. This will be

completed alongside the physical therapy they are receiving. Activities including running will be allowed as tolerated following published guidelines by [name].

In subjects who have bilateral AT, the leg with the most severe symptoms (determined by the VISA-A) will be chosen as the primary data for the study, however both legs will be treated consistent with the treatment group the subject was randomized into. Outcomes will be obtained for each Achilles tendon, regardless of treatment, using VISA-A at each data collection point. Participants will also be asked to complete a weekly log of running and completing PT exercises.

## Part 2

At the 3-month follow-up, participants who are not satisfied with their outcome will be given the option to choose one of the remaining treatment arms. Regardless of what treatment a patient chooses, if any, there will be one final visit conducted at 6 months for final data collection.

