## **VI. BIOSTATISTICAL ANALYSIS**

### **a. Specific data variables being collected**

#### *Questionnaires:*

- Symptoms severity specific to Achilles will be **VISA-A**

- The VISA-A is currently the only valid and reliable measure to assess function and pain in AT (validity,  $P < 0.01$ ; test-re-test reliability,  $r = 0.98$ ) (2\*)
- ProMIS-29 will be used to capture other aspects of non-disease specific measures of health-related domains (physical, mental and social health).
- The University of Wisconsin Running Injury and Recovery Index (**UWRI**) will measure aspects unique to the running population.
- Visual analog scale of pain
- To quantify patient choice and motivation for treatment, an unvalidated survey will be obtained to determine patient goals of enrollment in study and reason for selecting a different intervention.
- Patient satisfaction with treatment
- **Participant demographics**
  - **Age at enrollment**
  - **Gender**
  - **Fitzpatrick skin type**
  - **Self-identified race and/or ethnicity**
  - **Marital status**
  - **Military status**
  - **Exclusion Criteria**
  - **BMI calculated from height and weight**
  - **Achilles tendon surgical history**
- **Expected AE interview forms**
  - **Achilles specific (one for each limb at week 1 check in, week 2 check in, 3 week follow-up, 6 week follow-up, 3 month follow-up, and 6 month follow-up)**

*Ultrasound:* Ultrasound measures will be assessed at baseline, 3 months and 6 months. Measures of interest include cross-sectional area, degree of thickening within the tendon at site of maximal circumference and maximal pain, and presence and number of neovessels on color flow doppler.

*Function:* Quantitative function in heel raises to fatigue will be measured at baseline, 3 months and 6 months on both affected and unaffected limb. We will also ask the participants to complete 20 hops and rate their pain using a visual analog scale (0 to 10).

*Return to running:* We will be asking participants to record their return to running, following Drs. Silbernagel & Crossley protocol. In order to log this, they will track the date, exercise and pain level using the University of Delaware training diary.

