### **b. Study Endpoints**

Objective Endpoints

- Ultrasound endpoints
- Calf raises

Subjective Endpoints

- Questionnaires

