### **c. Statistical methods**

For the statistical analysis of both the primary outcome, VISA-A, and secondary outcomes, PROMIS-29, UWRI, VAS, ultrasound measurements, and functional tests, we will use the

Shapiro-Wilk test to for normality in the data. For the continuous data we will use the t-test and ANOVA test if the data is normally distributed, and we will use the Mann-Whitney U test and Kruskal-Wallis analyze the data that is not normally distributed. For the binary data we will use the chi or Fishers test to compare the data.

In the first phase of the study, the randomized control trial, we will use a multivariable linear regression, controlling for: sex, BMI, age, medical condition (thyroid disease and diabetes) and prior oral steroid and/or fluoroquinolone use. In phase 2 after the elective cross-over, we will use the models described above as repeated measure models.

Interim analysis will be performed after 30 participants are enrolled to review for safety and tolerance to treatment.

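### The ultrasound thickness site depends partly on where the tendon currently hurts, and the plan does not say whether it is one site or two, or fixed at baseline or found again at each visit

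*Combined protocol and SAP*

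**What the plan says.** The ultrasound paragraph of section VI.a sets the time points: "Ultrasound measures will be assessed at baseline, 3 months and 6 months". It lists cross-sectional area, thickening, and "presence and number of neovessels on color flow doppler". Of these, only thickening clearly carries a site rule: "degree of thickening within the tendon at site of maximal circumference and maximal pain". No section ties the site to an anatomical landmark or to the baseline scan, explains how the most painful point is found, or covers a participant without pain.

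Section VI.b puts "Ultrasound endpoints" under the objective endpoints. Section VI.c includes ultrasound among the "secondary outcomes, PROMIS-29, UWRI, VAS, ultrasound measurements, and functional tests"; VISA-A is primary. Section II expects every arm to show "improvement in functional outcomes, pain and measures of Achilles tendon structure compared to baseline measures". On blinding, section V.a says only that "patients will not be blinded to the treatment arm that they receive"; whether the person scanning is blinded is not stated.

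**The concern.** A change in thickness from baseline can be interpreted only if the same rule picks the measuring level at every visit and that rule does not depend on the outcome. Maximal circumference meets this condition. Maximal pain does not: it is a symptom, the treatments are meant to change it, and it can be located only through the participant, who knows the allocation. A self-reported, post-randomisation quantity thus helps decide where an endpoint labelled objective is measured.

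What is at stake is the interpretation of one secondary structural measure. Two operators could both follow the sentence faithfully and scan different levels. In a participant whose pain has resolved, one might leave the value blank and another might choose a level. Those gaps or choices would fall among participants who did well on pain, and could be unequal across arms.

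**Working it through.** **Plan's own figures.** The only related figure is the sample size: 3 arms × 20 = 60, which agrees with section IV.a. There is no power calculation and no ultrasound figure to reproduce, so the main check is textual.

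**Step 1: the four readings of the site rule.**

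| | Fixed at baseline | Found again at each visit |
|---|---|---|
| One site meeting both criteria | Same level each time, but undefined if the criteria disagree at baseline | No such site in a pain-free participant; left to the operator if the criteria disagree |
| Two separate sites | Both levels can be revisited whatever the later pain | Circumference site always exists; pain site may move or be absent |

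The text allows all four. The dependence on current pain arises in the right-hand column; the question of disagreement arises in the top row.

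**Step 2: the passages together.** Section II gives the link between treatment, structure and pain: "As SWT and PBMT may change structural properties and modulate pain in tendinopathy". Section V.a leaves participants unblinded. Sections VI.b and VI.c make ultrasound an objective, analysed outcome. If the site is found again at each visit, treatment can therefore influence where thickness is measured as well as the thickness itself. Pain-free participants are foreseeable, since sections II and VIII.a expect improvement in every arm.

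**Step 3: illustration of a moved site (assumed values).** Suppose the excess thickness over normal tendon falls off along the tendon as a Gaussian curve with standard deviation s. With no structural change, moving from the peak to a level d mm away gives an apparent loss of 1 − exp(−d²/(2s²)) of the peak excess.

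| s (assumed) | d = 5 mm | d = 10 mm |
|---|---|---|
| 10 mm | 11.8% | 39.3% |
| 15 mm | 5.4% | 19.9% |
| 20 mm | 3.1% | 11.8% |

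For example, with s = 10 and d = 10: 1 − exp(−100/200) = 0.393. The reverse move, from d mm off the peak at baseline to the peak later, gives a gain of the same size. A site found again at maximal circumference stays at the peak, and the error is then zero.

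**Step 4: illustration of lost values (assumed shares).** Suppose a share p of each arm is pain-free and goes unmeasured, so n = 20(1 − p). For a two-arm comparison at two-sided 5% (assumed) and 80% power, the detectable difference in SD units is (1.960 + 0.842) × √(2/n).

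| p | n per arm | Detectable difference |
|---|---|---|
| 0 | 20 | 0.89 |
| 10% | 18 | 0.93 |
| 20% | 16 | 0.99 |
| 30% | 14 | 1.06 |
| 50% | 10 | 1.25 |

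The lost precision matters less than the fact that the loss would depend on outcome, which no sample size repairs.

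**The case against.** The strongest reply is that the sentence names maximal circumference first. That site is anatomical and exists at every visit, so an operator who uses it has no difficulty. The sentence is also an item in a list of variables, not an imaging procedure, and its silence on relocating the site does not mean the pain site is found afresh. Both points stand, and they limit the finding to a pain-site value or one that needs both criteria at once. They do not remove it, because nothing in the text lets circumference override pain when the two differ.

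A reader might infer more: that the site is simply where it hurts most, that the endpoint disappears in pain-free participants, and that better pain relief in the device arms would move the site and produce false structural healing. The documents do not support this. Pain is only half of the definition. No section says that relief moves the most painful point; intensity and location are different things. A move could equally hide healing or look like worsening.

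The reply is also right that the consequence is limited. This is a pilot, and the structural hypothesis is a change from baseline; the between-arm expectation in section II concerns running function. Still, section VI.c covers ultrasound with group-comparison tests.

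Finally, re-measuring only at the level chosen as the baseline maximum would invite regression to the mean, and so apparent improvement in every arm. That objection is sound and shapes the fix.

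**Conclusion.** The point holds in limited form. The rule is ambiguous on one site or two and on fixed or found again, and it gives no instruction for disagreeing criteria or absent pain. Its pain criterion lets a treatment-sensitive symptom, reported without blinding, help set the location of a secondary endpoint called objective. This goes beyond missing detail, because a pain-independent site anchored to a landmark is a better method at very little cost.

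The size and direction of any bias cannot be stated. The 3.1% to 39.3% range for a 5 to 10 mm shift rests wholly on an assumed profile and an assumed shift; the detectable differences rest on assumed pain-free shares. Neither is an estimate for this trial. The maximal-circumference site, neovessels and VISA-A are unaffected, and cross-sectional area is not clearly tied to the pain site.

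**What to change.** In section VI.a, define the thickness endpoint as the maximal mid-portion thickness on the index tendon at each visit, found without reference to pain. The same search for the maximum then applies at all three visits, and the endpoint is a single named value.

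At baseline, also record the distance from the calcaneal insertion to the site of maximal thickness and, if it differs, to the most painful site. Re-measure at those recorded distances at 3 and 6 months whatever the current pain, and report the results as supporting values. This keeps the investigators' interest in the painful site while fixing its location. Supporting values at the baseline maximum should be read with regression to the mean in mind.

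The cost is a short change to the text, one or two fields on the ultrasound form and a few extra seconds per scan. No extra scan is needed and treatment is unchanged. A baseline distance that was not recorded may not be recoverable later, so the change is best made before further scans.

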### **b. Study Endpoints**

Objective Endpoints

- Ultrasound endpoints
- Calf raises

Subjective Endpoints

- Questionnaires

### **c. Statistical methods**

For the statistical analysis of both the primary outcome, VISA-A, and secondary outcomes, PROMIS-29, UWRI, VAS, ultrasound measurements, and functional tests, we will use the

Shapiro-Wilk test to for normality in the data. For the continuous data we will use the t-test and ANOVA test if the data is normally distributed, and we will use the Mann-Whitney U test and Kruskal-Wallis analyze the data that is not normally distributed. For the binary data we will use the chi or Fishers test to compare the data.

In the first phase of the study, the randomized control trial, we will use a multivariable linear regression, controlling for: sex, BMI, age, medical condition (thyroid disease and diabetes) and prior oral steroid and/or fluoroquinolone use. In phase 2 after the elective cross-over, we will use the models described above as repeated measure models.

Interim analysis will be performed after 30 participants are enrolled to review for safety and tolerance to treatment.

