## III. SUBJECT SELECTION

### a. Inclusion/Exclusion Criteria

#### Inclusion Criteria

Patients will be eligible if they meet the following criteria:

- Patients aged between 18-65 years old with a diagnosis of mid-portion Achilles tendinopathy (including both unilateral and bilateral)
- Running is the pre-injury primary form of physical activity and pre-injury would complete on average 10 miles per week or more of running
- VISA-A <80 at baseline to be eligible

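### The Part 1 regression for VISA-A leaves out baseline VISA-A, which costs precision at 20 per arm, and the plan does not say which Part 1 analysis, visit or contrast is primary

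*Combined protocol and SAP*

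**What the plan says.** Section VI.c (Statistical methods) names VISA-A as primary and lists PROMIS-29, UWRI, VAS, ultrasound and functional tests as secondary. For all of them it plans a Shapiro-Wilk check, and then: "For the continuous data we will use the t-test and ANOVA test if the data is normally distributed". Mann-Whitney U and Kruskal-Wallis are the alternatives.

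The next paragraph adds a model for Part 1: "In the first phase of the study, the randomized control trial, we will use a multivariable linear regression". The adjustment set for that model is then given as "controlling for: sex, BMI, age, medical condition (thyroid disease and diabetes) and prior oral steroid and/or fluoroquinolone use". Baseline VISA-A is not on that list. The section gives no order between the two approaches, no significance level and no primary visit or contrast. It does not say whether the outcome is the follow-up value or the change.

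Other sections fill in part of this:
- Baseline VISA-A exists for everyone. The Inclusion Criteria require "VISA-A <80 at baseline to be eligible", and Table 2 collects VISA-A at baseline, 3 weeks, 6 weeks, 3 months and 6 months.
- Section II places the end of the randomised comparison at 3 months: "After the initial 3-month randomized control trial", dissatisfied participants may choose another arm.
- Section II states two kinds of hypothesis. One is within-arm: "improvement in functional outcomes, pain and measures of Achilles tendon structure compared to baseline measures". The other is between arms: "we anticipate greater measures in running function for participants assigned to SWT and PBMT in treatment over physical therapy as sole treatment".
- Section V.a fixes the leg for bilateral disease: "the leg with the most severe symptoms (determined by the VISA-A) will be chosen as the primary data for the study".
- Sections IV.a and V.a plan 20 per arm, 60 in all. Section V.a says there is no power calculation because this is a feasibility study.

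**The concern.** Two separate matters are involved.

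The first is precision. The baseline value of an outcome score is usually its best single predictor. With 20 per arm the intervals will be wide, and the planned model adjusts for five listed factors but not for the score itself. That widens the interval for the primary comparison and leaves a chance baseline difference between arms uncorrected, although the data to prevent both are already being collected.

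The second is interpretation. With two analyses of one primary outcome and no order between them, a reader of the results cannot tell whether a p-value below 0.05 is the planned test or one of several. In a three-arm trial the t-test could also mean pairs of arms or change within an arm, and Section II hypothesises both kinds of effect.

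**Working it through.** **No figure to reproduce.** The plan states no error rate, power or standard deviation (SD). What follows uses the design (3 arms of 20) and stated assumptions.

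**A. Cost of omitting baseline VISA-A**

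Inputs: n = 20 per arm; equal SD across arms; assumed correlation r between baseline and 3-month VISA-A.

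1. Unadjusted 95% half-width for a pairwise difference, in SD units: t(57) × √(2/20) = 2.002 × 0.316 = 0.63.
2. The planned regression, if its covariates are unrelated to outcome: intercept, 2 arm terms and 6 covariate terms (thyroid disease and diabetes entered separately) leave 60 − 9 = 51 degrees of freedom, and 2.008 × 0.316 = 0.63. The starting point is the same.
3. Adding baseline leaves 50 degrees of freedom and multiplies the standard error by √(1 − r²). The half-width is 2.009 × 0.316 × √(1 − r²).

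| Assumed r | √(1 − r²) | SE reduction | 95% half-width (SD) |
|---|---|---|---|
| 0.3 | 0.954 | 5% | 0.61 |
| 0.5 | 0.866 | 13% | 0.55 |
| 0.6 | 0.800 | 20% | 0.51 |
| 0.8 | 0.600 | 40% | 0.38 |

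The formula ignores chance imbalance in covariates. Simulation with age, sex and BMI in the model, unrelated to outcome, gave 3.6%, 12.4%, 18.9% and 39.1%.

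4. The gain changes if the other covariates matter. Suppose they explain 20% of outcome variance.
 - If they also explain 20% of baseline variance in the same direction, the partial correlation is (r − 0.2)/0.8. For r = 0.3, 0.5 and 0.8 that is 0.125, 0.375 and 0.75, and the reductions are 1%, 7% and 34% (about 0%, 6% and 33% in simulation).
 - If they are unrelated to baseline, the partial correlation is r/√0.8, and the reductions are 6%, 17% and 55% (about 5%, 16% and 55% in simulation).

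**B. False-positive chance for VISA-A at 3 months**

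Assumptions: no true difference, normal outcome, two-sided 5% per test, no Shapiro-Wilk switching. These are null simulations with 12,000 to 20,000 trials per setting. The regression had six covariate terms, and the covariate R² was set at 0, 0.1, 0.2, 0.3 and 0.4.

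| Reading of the plan | Chance of at least one false positive |
|---|---|
| One global three-arm test, either analysis alone | about 5% |
| Global test from either analysis | 6.6% to 8.5% |
| Two contrasts against physical therapy, one analysis | about 9% |
| The same two contrasts, either analysis | 11.5% (R² = 0) to 14.4% (R² = 0.4) |
| All three pairs, t-tests only | about 12% |
| All three pairs, either analysis | 15.3% (R² = 0) to 19.0% (R² = 0.3 and 0.4) |

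Checks: three pooled-variance pairwise tests, from the studentized range at 2.002 × √2 = 2.83 with 3 groups and 57 degrees of freedom, give 12.1%. If the tests were independent, two would give 1 − 0.95² = 9.75% and three would give 1 − 0.95³ = 14.3%. The simulated single-analysis figures lie just below these, as they should when contrasts share an arm.

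**The case against.** **This is a pilot.** Section V.a says there is no power calculation, and no significance threshold is promised anywhere. That stands, and it lowers the weight of part B. It does not remove the point: Section I says the study will assess the most effective treatment, Section II makes treatment effects the primary aim with a directional expectation, and Section VI.c plans inferential tests. Precision matters in a pilot as well, since its estimates are the main product.

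**Section VI.c can be read as ranked.** The tests may be generic for all outcomes, with the regression as the one model for the randomised phase. This is a fair reading. Under it the false-positive chance is about 5% for a global test or 9% for two contrasts. The text does not say so, and one sentence would settle it.

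**Stronger readings that the documents do not support:**
- A reader might infer that the missing covariate raises the false-positive rate. In a randomised comparison it does not; the cost is precision.
- A reader might infer that the plan gives no idea of visit or contrast. Section II and Section V.a point to 3 months and to comparisons with physical therapy alone. Only a formal designation is missing.
- A reader might take 15-19% as the plan's error rate. That needs all three pairs and either analysis to count, which is not the reading closest to Section II. It is not a ceiling either: three pairwise t-tests on both the value and the change give about 21% at an assumed correlation of 0.5. Counting every visit as well gives larger figures, but nothing in the plan says that any visit may carry the claim.
- A reader might put a figure on the Shapiro-Wilk switch. The plan does not say whether it is applied per arm, pooled or to residuals, or at what level, so any figure rests on a rule that the plan does not contain.
- A reader might infer that thyroid disease, diabetes and prior steroid or fluoroquinolone use cannot be fitted because Section VI.a does not name them. Not being named there does not show that they are not collected.

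**Conclusion.** The point holds in two parts of unequal weight. The firmer part is the omission of baseline VISA-A from the Part 1 regression. The gain from including it depends on a correlation that the documents do not give: about 5% off the standard error at 0.3 and 40% at 0.8, somewhat more or less if the other covariates are related to outcome or baseline. The half-width for a pairwise difference falls from 0.63 SD to between 0.61 and 0.38 SD.

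The second part is the missing designation of one primary analysis, visit and contrast. On the reading closest to the stated aims, two contrasts against physical therapy at 3 months, the false-positive chance is about 9% with one analysis and about 12-14% if either may be used. This assumes two-sided 5% per test and covariate R² from 0 to 0.4. In a feasibility study it is a matter of clear reporting more than of error control. Both parts should be put right before outcome data are examined; neither threatens the design.

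**What to change.** In Section VI.c:

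1. Make the linear regression already planned the single primary Part 1 analysis of VISA-A at 3 months in the index leg defined in Section V.a. Fit arm and baseline VISA-A together with the planned covariates. With baseline in the model, the arm contrasts are the same whether the outcome is the value or the change, so that ambiguity closes too.
2. Say which score is the baseline covariate. It should precede treatment; Table 1 lists VISA-A at the first week-1 visit, which is also the first treatment visit in both shockwave arms.
3. Report the two contrasts against physical therapy alone with 95% confidence intervals.
4. Label the t-test/ANOVA and rank tests, the 3- and 6-week visits, within-arm change and the other outcomes as supportive or exploratory.
5. Either state how the two contrasts share the error rate, or state that all tests are exploratory and make no significance claims.

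A three-arm test as a gate before the contrasts is optional because it costs power. In a simulation with 20 per arm and a true 0.8 SD contrast, power fell from 70% to 58% with arm means of 0, 0.4 and 0.8 SD; with means of 0, 0 and 0.8 SD it was 64%.

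The cost is wording and one degree of freedom. No new data are needed, since Table 2 already collects VISA-A at baseline and 3 months. The other tests lose their standing as possible primary results.

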## IV. SUBJECT ENROLLMENT

### a. Recruitment Procedure

We hope to enroll 60 runners into three treatment arms (n=20 in each arm). We will be using a multi-pronged approach to recruit patients:

- Running Clinics
  - Referral from [name]
  - Referrals from other physicians at MGB and Harvard affiliated hospitals
    - A letter and flyer will be provided to other practitioners in the MGB network to ask them to refer our study information to their patients.
- Social Media
- Email Lists
  - Flyers to be sent to different email lists of running clubs
- Hospital advertising
  - Flyers
  - Rally
  - Research Patient Data Registry (RPDR)

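### A Shapiro-Wilk test on the outcome data chooses between means and ranks for VISA-A and every continuous secondary outcome, and the plan does not say whether that comparison or the adjusted regression is the primary result

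*Combined protocol and SAP*

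**What the plan says.** Section VI.c (Statistical methods) begins "For the statistical analysis of both the primary outcome, VISA-A, and secondary outcomes, PROMIS-29, UWRI, VAS, ultrasound measurements, and functional tests, we will use the" and continues "Shapiro-Wilk test to for normality in the data". The result of that test picks the comparison: "For the continuous data we will use the t-test and ANOVA test if the data is normally distributed", and in the other case "we will use the Mann-Whitney U test and Kruskal-Wallis analyze the data that is not normally distributed". The section gives no significance level for the normality test. It does not say whether the test is applied to each arm, to all arms pooled, to residuals or to changes from baseline. It has no rule for arms that give different answers.

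The next paragraph plans a second analysis: "In the first phase of the study, the randomized control trial, we will use a multivariable linear regression, controlling for: sex, BMI, age, medical condition", with prior oral steroid or fluoroquinolone use also in the list. This sentence carries no normality condition. It names no outcome, visit or treatment term, and baseline VISA-A is not among the covariates. For the later phase, "In phase 2 after the elective cross-over, we will use the models described above as repeated measure models", without saying which of them.

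Section VI.c calls VISA-A the primary outcome. It names neither a primary time point nor which of the two analyses is primary. On size, Section V.a says: "There will be 20 patients per treatment group, no power calculation as this is a feasibility study". Table 2 lists VISA-A at baseline, 3 weeks, 6 weeks, 3 months and 6 months, so four of the five assessments fall in Part 1. Section III.a limits entry to a VISA-A score below 80.

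**The concern.** The two routes answer different questions. A t-test or ANOVA concerns a difference in mean points. Mann-Whitney and Kruskal-Wallis, as listed, concern a shift in ranks and come with no size in points. When a test on the outcome data makes the choice, the data being compared select the quantity reported.

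Three features make switching likely here:

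- A linear comparison needs roughly normal residuals, not a normal pooled outcome. If arms differ, or scores bunch near the top of the scale, pooled values can fail the test when the residuals would pass.
- With 20 per arm, arm-wise verdicts are noisy and can conflict.
- The entry limit truncates VISA-A at baseline, while Section II expects improvement in every arm. The shape of the distribution should therefore change between visits.

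At stake is the main comparative output of a 60-person pilot, a treatment difference that can be read on one scale across visits and outcomes.

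**Working it through.** **Inputs from the documents.** Three arms of 20 (3 × 20 = 60, which agrees with Section IV.a), and four VISA-A assessments in Part 1 (Table 2). There is no power calculation, VISA-A mean, SD or Shapiro-Wilk level, so there is no figure of the plan's own to reproduce.

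**Assumptions.** Shapiro-Wilk at 5%; scores capped at 100; means, SDs and visit correlations as shown below.

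**1. Exactly normal data, tested arm by arm, any failure sending the comparison to ranks.**

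- One visit, 3 tests: 1 − 0.95³ = 0.143 (simulated 0.143).
- Three arms at four visits, 12 tests treated as independent: 1 − 0.95¹² = 0.460.
- Visits on the same runners are correlated. Simulated with correlations from 0.3 to 0.8, the method differs between at least two of the four visits in 46% to 41% of trials.
- Exactly one arm fails in about 14% of trials, so pairwise contrasts could use different methods at the same visit.

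**2. Capped scores, arms with different means (3,000 to 4,000 simulated trials per setting; ranges cover repeat runs).**

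| Setting (arm means, SD) | Pooled values fail | Residuals fail | Some but not all arms fail |
|---|---|---|---|
| 3 weeks: 60/61/62, SD 15 | 4–5% | – | – |
| 3 months, milder: 70/76/78, SD 16 | 26–27% | 12–14% | 20–22% |
| 3 months: 72/80/82, SD 18 | 80% | 40–42% | 53–54% |

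In the last row, the unstated choice between testing pooled values and testing residuals moves the failure rate from 80% to about 41%. Two analysts following the same text could reach different methods.

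The rates depend strongly on the assumptions. At SD 15, pooled values fail in 46% of trials for 72/80/82, 13% for 70/75/77 and 5% for 65/70/72.

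**3. Capped scores, equal arm means, SD 15.** At least one arm fails in 15% of trials with mean 75 and in 73% with mean 85.

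**4. Effect on the inference.**

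- For means of 72 v 82 with SD 18, power is 0.40 for the t-test and 0.38 for Mann-Whitney. They disagree on significance in about 6% of trials.
- With no true difference, the two-stage ANOVA/Kruskal-Wallis procedure rejects in 5.4% to 5.8% of trials. The simulation error is √(0.05 × 0.95 / 4000) = 0.3 percentage points, so this is close to nominal. ANOVA and Kruskal-Wallis disagree in 2% to 3% of these trials.

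**5. What a fixed linear analysis gives.** The unadjusted 95% half-width for 20 v 20 is t(0.975, 38 df) × SD × √(2/20) = 2.02 × SD × 0.316. That is 6.4, 9.6 and 12.8 points for assumed SDs of 10, 15 and 20, on one scale at every visit.

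**The case against.** The strongest reply is that the regression already protects the result. Section VI.c commits the randomized phase to a multivariable linear model with no normality condition, so on a plain reading an adjusted mean difference is produced whatever Shapiro-Wilk shows. That stands. A reader might infer that a failed normality test strips the 3-month VISA-A result of its effect estimate and its covariates. The documents do not support this. The regression is outside the gate as written. The t-test and ANOVA route is itself unadjusted, so moving to ranks removes no covariate. The effect estimate would be lost only if the gated test were the headline, or if the gate were meant to cover the regression. The plan neither says nor excludes either.

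It can also be said that the section promises no confidence interval for the t-test or ANOVA, so a missing interval is not specific to the rank route. That is correct; it is a general reporting gap that the same edit can close.

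Finally, the practical effect is modest: little difference in power, about 6% disagreement, error rates near nominal, and a study described as a feasibility study. The failure rates rest on values the plan does not give and fall to about 5% when scores stay well below the cap. This limits the severity. It does not remove the data-driven choice or settle which analysis is primary.

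**Conclusion.** The point holds for the unadjusted comparison. The rule lets the data choose between a mean difference and a rank comparison for VISA-A and each continuous secondary outcome, and the choice can change across visits, outcomes and pairwise contrasts. It is also under-specified, because neither the level of the normality test nor the data it applies to is stated.

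In the two 3-month settings simulated with unequal arms and SDs of 16 and 18, the gate sends pooled VISA-A to ranks in about 25% to 80% of trials, or in 12% to 42% if residuals are tested. Smaller spreads and lower means give less.

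The consequence is an unstable estimand, and uncertainty about which number will be the headline, because a gated unadjusted test stands beside an ungated adjusted regression with neither named primary. The carry-over of the earlier models into the cross-over phase adds to this, since Mann-Whitney and Kruskal-Wallis have no direct repeated-measures form. The calculations show no material type I error inflation. This is an inexpensive improvement that should be made, not a flaw that invalidates the trial.

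**What to change.** In Section VI.c:

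1. Delete the Shapiro-Wilk gate.
2. Name the linear regression already planned as the primary analysis of VISA-A at 3 months, the end of Part 1. Include treatment arm and baseline VISA-A as explicit terms; baseline VISA-A is already collected.
3. Report arm differences in points with 95% intervals that are robust to non-normality. Choose one method in advance, for example the bootstrap.
4. Use the same model for the other continuous outcomes at each follow-up visit where they are measured. State that the Part 2 repeated-measures analysis extends this linear model.
5. Check residuals by plot, as a diagnostic that does not change the primary method.
6. Keep one rank-based comparison as a pre-specified sensitivity analysis.
7. Analyse neovessel number with a count or ordinal model, named in advance.

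The cost is a revision of the statistical text and a little more analysis work. No extra participants, visits or measurements are needed.
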